5.7 Schedule of assessments

Table 5–1: Schedule of assessments

Study Period	SCR	Treatment Period								Treatment Extension Period								SFU ^a
Visit ^b /Week (Visit window ± 3 days)	V1	V2	V3	V4	V5	V6	V7	V8	V9	V10	V11	V12	V13	V14	V15	V16	V17	V18
Procedures	SV	BL W0	W2	W4	W6	W8	W10	W12	W16	W20	W24	W28	W32	W36	W40	W44	W48 /WD	W64
Written informed consent ^c	X																	
Demographic data	X																	
AS history	X																	
Inclusion/exclusion criteria	X	X ^d																
Significant past medical history and concomitant diseases	X	X ^e																
Prior and concomitant medications ^f	X	X	X	X	X	X	X	X	X	X	X	X	X	X	X	X	X	X
Adverse events	X	X	X	X	X	X	X	X	X	X	X	X	X	X	X	X	X	X
C-SSRS	X	X	X	X	X	X	X	X	X	X	X	X	X	X	X	X	X	X
HADS	X	X		X	X			X	X	X	X	X	X	X	X	X	X	X
BASDAI	X	X	X	X	X	X	X	X	X	X	X	X	X	X	X	X	X	X
BASFI	X	X	X	X	X	X	X	X	X	X	X	X	X	X	X	X	X	X
PGADA		X	X	X	X	X	X	X	X	X	X	X	X	X	X	X	X	X
PhGADA		X	X	X	X	X	X	X	X	X	X	X	X	X	X	X	X	X
Total and nocturnal spinal pain (NRS)	X	X	X	X	X	X	X	X	X	X	X	X	X	X	X	X	X	

Table 5–1: Schedule of assessments

Study Period	SCr	Treatment Period								Treatment Extension Period								SFU ^a
Visit ^b /Week (Visit window ± 3 days)	V1	V2	V3	V4	V5	V6	V7	V8	V9	V10	V11	V12	V13	V14	V15	V16	V17	V18
Procedures	SV	BL W0	W2	W4	W6	W8	W10	W12	W16	W20	W24	W28	W32	W36	W40	W44	W48 /WD	W64
Physical examination (incl. height and weight) ^g	X							X			X			X			X	
Vital signs (BP, pulse, temperature) ^h	X	X	X	X	X	X	X	X	X	X	X	X	X	X	X	X	X	
12-lead ECG (local)	X	X		X		X		X	X	X	X	X	X	X	X	X	X	
Tuberculosis questionnaire	X							X			X			X			X	
IGRA TB test ⁱ	X																X	
Pregnancy test ^j	X	X		X		X		X	X	X	X	X	X	X	X	X	X	
Hematology/biochemistry/urinalysis ^k	X	X	X	X	X	X	X	X			X			X			X	
Serology (HIV, Hepatitis B and C, HLA-B27) ^{k,l}	X																	
Blood samples for cytokines, complement, and biomarker analysis ^k		X		X				X			X			X			X	
Blood sampling for bimekizumab and CZP plasma concentrations ^k		X		X				X			X			X			X	
Bimekizumab and CZP antibody detection ^k		X		X				X			X			X			X	

Table 5–1: Schedule of assessments

Study Period	SCR	Treatment Period								Treatment Extension Period								SFU ^a
Visit ^b /Week (Visit window ± 3 days)	V1	V2	V3	V4	V5	V6	V7	V8	V9	V10	V11	V12	V13	V14	V15	V16	V17	V18
Procedures	SV	BL W0	W2	W4	W6	W8	W10	W12	W16	W20	W24	W28	W32	W36	W40	W44	W48 /WD	W64
Blood sample for hs-CRP ^k	X	X		X		X		X	X	X	X	X	X	X	X	X	X	X
Blood samples for pharmacogenetic variables		X						X									X	

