8.11 Week 48 (Visit 17)/Early Withdrawal Visit

- Record prior and concomitant medications.
- Assess adverse events.
- C-SSRS.
- HADS.
- Determine the BASDAI.
- Determine the BASFI.
- Perform the PGADA.
- Perform the PhGADA.
- Total and nocturnal spinal pain (NRS).
- Measure vital signs (temperature, pulse, and blood pressure).
- Perform a 12-lead ECG.
- Perform a physical examination, including an evaluation for signs and symptoms of active TB and risk for exposure to TB and weight.
- Perform a 12-lead ECG.
- Administer the tuberculosis questionnaire.
- Perform an IGRA tuberculosis test (QuantiFERON TB test).
- Perform a urine pregnancy test.
- Collect samples for:
 - Hematology/biochemistry/urinalysis.
 - Bimekizumab and CZP plasma concentrations.
 - Anti-bimekizumab and anti-CZP antibody detection.
 - hs-CRP.

- If the respective ICF has been provided collect blood samples for:
 - Cytokines, complement, and biomarker analyses.
 - Pharmacogenetic variables.
 - Nonhereditary pharmacogenomic variables.

- Collect urine samples for biomarker research if the respective ICF has been provided.
- Obtain a X-ray or CT scan of the chest if the QuantiFERON TB test returned a positive result.
- Perform a PET-MRI or PET-CT scan in at least 25 subjects at selected sites within 2 weeks after the Week 48/WD Visit if PET-positive lesions were observed in the previous scan. At the WD Visit, the PET-MRI or PET-CT must be done only, if the previous imaging evaluation occurred more than 12 weeks ago and if PET-positive lesions were observed in the previous scan.
- Record visit in the IRT.

8.12 Safety Follow-Up Visit (Week 64, Visit 18, 20 weeks after the final dose of IMP)

- Record concomitant medications.
- Assess adverse events.
- Measure vital signs (temperature, pulse, and blood pressure).
- Perform a 12-lead ECG.
- Administer the tuberculosis questionnaire.
- Perform a urine pregnancy test.
- Collect samples for:
 - Hematology/biochemistry/urinalysis.
 - Bimekizumab and CZP plasma concentrations.
 - Anti-bimekizumab and anti-CZP antibody detection.
 - hs-CRP.
- If the respective ICF has been provided collect blood samples for:
 - Cytokines, complement, and biomarker analyses.
 - Nonhereditary pharmacogenomic variables.
- Record visit in the IRT.

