## 2.3 Study design and conduct

AS0013 is a multicenter, randomized, subject-blind and investigator-blind, parallel-group study to evaluate the efficacy and safety of BKZ compared to CZP in adult subjects with active adult-onset AS.

It is planned that at least 60 subjects will be randomized to 1 of 2 treatment arms in a 2:1 ratio and will receive either BKZ or CZP up to Week 44 (final dose of investigational medicinal product [IMP]).

The study will include a Screening Period of 2 to 4 weeks, a 12-week Treatment Period, a 36-week Treatment Extension Period, and a 20-week Safety Follow-up (SFU) Period (starting after the final dose of IMP). Therefore, the maximum duration of the study will be 68 weeks.

At the start of the Treatment Period, eligible subjects will be randomized in a 2:1 ratio to receive the following blinded study treatments:

- BKZ 160mg sc Q2W from Week 0 through Week 10. In addition, subjects will receive 1 placebo injection at Baseline (Visit 2), Week 2 (Visit 3), and Week 4 (Visit 3) in order to maintain the blind versus the CZP loading dose at these visits.
- CZP 400mg sc Q2W at Weeks 0, 2, and 4 (loading dose) followed by CZP 200mg sc Q2W at Weeks 6 to 10.

After completing the 12-week Treatment Period, subjects will enter a 36-week Treatment Extension Period and will receive the following treatments:

- Subjects randomized to BKZ during the Treatment Period will receive BKZ 320mg sc every 4 weeks (Q4W) from Week 12 to Week 44.
- Subjects randomized to CZP during the Treatment Period will receive CZP 400mg Q4W from Week 12 to Week 44.

Subjects not responding to treatment during the Treatment Period will be withdrawn from the study as per Investigator's discretion and will not enter the Treatment Extension Period.

In a substudy of AS0013, a PET-MRI or PET-CT scan of the entire spine will be performed at selected sites in approximately 25 subjects at Screening and during the study at Week 12 and Week 48 or Early Withdrawal Visit if PET positive lesions were observed in the previous scan.

All subjects who complete the study or who discontinue from the study early, including those withdrawn from the IMP treatment, will have a SFU Visit at 20 weeks after their final dose of IMP.

Three unblinded interim analyses will be conducted:

- Interim Analysis 1 (IA1): when approximately 45 subjects have completed the Week 4 visit during the Treatment Period.

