## 10 IMMUNOLOGICAL ANALYSES

The results for the ADA measurements will be listed by treatment group and time point based on the SS, including the Screening assay, confirmatory assay and titre (if applicable).

A cut point will be determined by the bioanalytical laboratory that will be used to determine the status of ADA as above the cut point (ACP) or below the cut point (BCP). For any ADA levels that are ACP, a further confirmatory assay will be performed, the results of which will be determined as either 'confirmed positive' (CP) or 'not confirmed positive' (NCP). For samples that are CP, a further titre assay will be performed and the ADA titre will be reported. The following definitions will be applied:

- An ADA status for a given time point of positive will be concluded for any subject with an ADA level that is ACP and CP at any time point
- An ADA status of negative for a given time point will be concluded for any subject with an ADA level that is either BCP or ACP and NCP at any time points
- A subject will be classified as having ADA positivity at Baseline if the Visit 2 (Week 0), pre-dose result is ACP and CP
- A subject will be classified as having treatment-induced ADA positivity when meeting 1 of the following criteria:
  - The Baseline result is either BCP or ACP and NCP, and at least 1 post-Baseline time point is ACP and CP
  - The Baseline result is positive (ACP and CP) and at least 1 post-Baseline measurement shows a pre-defined fold increase in titre from the Baseline value (the fold increase from Baseline required to meet this criterion will be defined with the development of the assay and will be included in the TFLs)
- A subject will be classified as overall positive if at least 1 post-Baseline measurement is ACP and CP (this includes subject who have negative results at Baseline)
- A subject will be classified as overall negative if at all post-Baseline visits the ADA status is negative (this includes subjects who have positive [ACP and CP] results at Baseline)

The ADA status (positive/negative) will be summarized as a categorical endpoint (number and percentage of subjects) by treatment group, for all time points and overall, based on the PK-PPS. In addition, the first occurrence of treatment-induced ADA positivity (based on the definitions

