### 11.2 Adverse events

Adverse events with start date prior to the first dose of IMP are defined as pre-treatment AEs. Adverse events with a start date prior to the first dose of IMP will be defined as pre-treatment AEs. A treatment-emergent AE (TEAE) is defined as any AE with a start date/time at the time of

or after the first dose of IMP up until 140 days after the last dose of IMP. Any AE with onset later than 140 days after the last dose of IMP will not be considered as treatment-emergent and therefore will not be included in the tabulations of TEAEs. Selected summaries will be presented separately for TEAEs during the Treatment Period (any AE with a start date/time at the time or after the first dose of IMP up until the Week 12 Visit) and TEAEs during the study (as per the definition of TEAEs given above).

Where dates are missing or partially missing, AEs will be assumed to be treatment-emergent, unless there is clear evidence to suggest that the AE started prior to dosing or later than 140 days post-last dose. Handling of missing dates/times for classification of AEs as TEAEs is described in [Section 4.2.5](#).

All AEs will be recorded in the eCRF from informed consent until study completion or termination. All AEs will be coded and categorized by intensity (mild/moderate/severe) and relationship to IMP (related/not related).

An overview of the number and percentage of subjects who experience TEAEs will be presented by treatment group, based on the SS. Separate tabulations will be presented for TEAEs during the Treatment Period and TEAEs during the study and will include the number and percentage of subjects with any TEAEs, serious TEAEs, related TEAEs, discontinuation due to TEAEs, severe TEAEs, AEs leading to death and TEAEs leading to death; event counts will also be included. The summary of TEAEs during the study will be repeated for subjects in the SS who were randomized in the PET-MRI/PET-CT substudy.

In addition, the following summaries will be presented by treatment group, SOC, high level term (HLT) and PT, based on the SS:

- Incidence of TEAEs[a] [b]
- Incidence of TEAEs, stratified by overall ADA status (positive/negative) as defined in [Section 10](#)
- Incidence of serious TEAEs[a] [b]
- Incidence of non-serious TEAEs[b]
- Incidence of TEAEs by relationship
- Incidence of TEAEs by maximum relationship
- Incidence of TEAEs by maximum intensity

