- Incidence of fatal TEAEs by relationship
- Incidence of non-serious TEAEs by relationship
- Incidence of serious TEAEs by relationship
- Incidence of non-serious TEAEs above threshold of 5% of subjects
- Incidence of non-serious TEAEs above threshold of 5% of subjects by relationship
- Incidence of TEAEs by SOC and PT (including the number and percentage of subjects and individual subject numbers for each PT stratified by intensity, relationship and seriousness)

[a] These summaries will be presented separately for TEAEs during the Treatment Period and TEAEs during the study.

[b] These summaries will be repeated for subjects in the SS who were randomized in the PET-MRI/PET-CT substudy and will be based on TEAEs during the study

In addition, separate summaries by treatment group, SOC, HLT and PT will be included for the following AEs for special monitoring (AESM):

- Major cardiovascular events
- Serious infections, including opportunistic infections and tuberculosis (TB)
- Malignancies including lymphoma
- Cytopenias
- Neuropsychiatric events
- Inflammatory bowel disease
- Anaphylactic reaction (hypersensitivity and anaphylactic reactions)
- Hepatic events and drug-induced liver injury

The criteria for identifying and additional criteria for reporting AESM are provided in [Section 14.5](#).

All summary tables (including those for AESM) will contain the number and percentage of subjects and the number of events where applicable. A subject who has multiple events in the same SOC, HLT and PT will be counted only once in the subjects counts but all events will be included.

In summaries including relationship to IMP, the following relationship categories will be included:

- Related
- Not related

Subjects who experience the same event multiple times will be included in the most related category for tabulations by maximum relationship. Events with missing relationship will be considered as 'Related' for summary purposes but shown as missing in the data listings.

In summaries including intensity, the following categories will be summarized:

- Mild
- Moderate
- Severe

Subjects who experience the same event multiple times will be included in the most severe category for tabulations by maximum intensity. Events with missing intensity will be considered as 'Severe' for summary purposes. All data will be presented as recorded in the database for the listings.

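### The planned TEAE-by-ADA table uses an ever-positive status with no timing, so events before the first positive sample count as ADA-positive; a before/after split should be added

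*SAP*

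**What the plan says.** SAP Section 11.2 lists, by treatment group in the Safety Set, "Incidence of TEAEs, stratified by overall ADA status (positive/negative) as defined in" Section 10. Section 10 sets the two strata:

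- Positive: "A subject will be classified as overall positive if at least 1 post-Baseline measurement is ACP and CP".
- Negative: "A subject will be classified as overall negative if at all post-Baseline visits the ADA status is negative".

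Neither definition refers to when an adverse event started. Section 10 also defines treatment-induced positivity: either a negative Baseline followed by a confirmed positive, or a positive Baseline followed by a pre-defined fold increase in titre. The adverse event table does not use that definition.

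A TEAE is any event starting at "or after the first dose of IMP up until 140 days after the last dose of IMP". SAP Section 2.3 says subjects "will receive either BKZ or CZP up to Week 44 (final dose of investigational medicinal product" (closing bracket omitted). Footnote [a] in Section 11.2 reads "These summaries will be presented separately for TEAEs during the Treatment Period and TEAEs during the study", but the ADA-stratified table does not carry that footnote, so the study-wide TEAE definition applies to it.

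In Protocol Table 5-1, the row "Bimekizumab and CZP antibody detection" is marked at Baseline and Weeks 4, 12, 24, 36 and 48/Early Withdrawal, and is blank at the Safety Follow-Up (SFU) Visit. Protocol Section 8.12 nevertheless lists the same sample at that visit, in the wording that Section 8.11 uses for Week 48 ("Anti-bimekizumab and anti-CZP antibody detection").

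**The concern.** The stratifying variable is settled by what happens after randomization, sometimes long after the events it is used to classify. An injection reaction at Week 2 in a subject first positive at Week 48 is tabulated as an ADA-positive event. Two things follow.

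- Events from before the first detected antibody are added to the ADA-positive stratum and can blur a real association.
- Subjects who stay longer have both more ADA samples and more time for TEAEs, so the two can be linked without any effect of antibodies. Protocol Section 5.1.3 makes unequal follow-up likely, because non-responders may be withdrawn at the end of the 12-week Treatment Period at the Investigator's discretion.

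Immunogenicity of bimekizumab is a stated objective, and this is the only planned summary that relates antibodies to adverse events. The hypersensitivity and anaphylaxis table (SAP Section 14.5.7) is not split by ADA, and the described content of the adverse event listings does not include ADA status.

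**Working it through.** The documents give no figure for this table, so there is nothing to reproduce.

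**Window for a completer.** The last dose is at Week 44, which is Day 308. Adding 140 days gives Day 448, or Week 64.

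**Share of that window before the first positive sample** = (7 × week of first positive) / 448:

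| First positive | Calculation | Share |
|---|---|---|
| Week 4 | 28/448 | 6% |
| Week 12 | 84/448 | 19% |
| Week 24 | 168/448 | 38% |
| Week 36 | 252/448 | 56% |
| Week 48 | 336/448 | 75% |
| Week 64, if sampled | 448/448 | 100% |

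**Unequal follow-up.** A non-responder last dosed at Week 10 has a TEAE window of 10 + 20 = 30 weeks and two post-Baseline ADA samples on Table 5-1 (Week 4 and Week 12/Early Withdrawal). A completer has 64 weeks and five. A subject leaving between Weeks 12 and 24 has three (Weeks 4, 12 and withdrawal). Each count rises by one if the SFU sample is taken.

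**Effect on the comparison, by simulation.** None of these inputs is in the documents: 20% to 50% of subjects seroconvert, either evenly over 48 weeks or mostly early; background hazard is constant, with 15% incidence over the window; dropout is 0% to 30%; the hazard ratio after seroconversion is 1, 2 or 3. There were 300,000 subjects per scenario. The SFU sample and Baseline-positive subjects were not modelled. Ranges run over the seroconversion settings.

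| True hazard ratio | Dropout | Ever-positive split: incidence ratio | Split at first positive sample: rate ratio |
|---|---|---|---|
| 1 | 0% | 1.01–1.02 | 1.00–1.03 |
| 1 | 15% | 1.02–1.08 | 0.98–1.02 |
| 1 | 30% | 1.06–1.12 | 0.98–1.03 |
| 2 | 0% | 1.52–1.72 | 1.86–1.97 |
| 2 | 30% | 1.69–1.83 | 1.88–1.97 |
| 3 | 0% | 2.03–2.31 | 2.67–2.91 |
| 3 | 30% | 2.24–2.46 | 2.65–2.93 |

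The first row agrees with 1, within simulation error. That is also the theoretical result: if follow-up is equal and antibodies have no effect, event incidence does not depend on the stratum.

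Not all of the shortfall from 2 comes from timing. A ratio of cumulative incidences falls below the hazard ratio anyway. With antibodies present from Day 0 it would be (1 − 0.85²)/0.15 = 0.2775/0.15 = 1.85. Timing accounts for the step from 1.85 to 1.52–1.72. For an event with 60% base incidence the corresponding figures are (1 − 0.4²)/0.6 = 1.40 and 1.29.

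With 15% incidence and no ADA effect, about 27% (early seroconversion) to 48% (even seroconversion) of ADA-positive subjects with the event had it before their first positive sample.

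**The case against.** The strongest reply is that little depends on this table. Protocol Section 3.3 classes immunogenicity as an other exploratory objective. Protocol Section 15.7 asks only for ADA summaries and positivity rates. SAP Section 3.1 confines formal testing to the primary and secondary efficacy variables. With 60 to 72 subjects randomized 2:1 (40 to 48 on bimekizumab, 20 to 24 on CZP), a shift of 6% to 12% in a ratio could not be told from noise. Adverse event onset dates, ADA results by time point and individual titre plots are all to be produced, so timing could be checked case by case. All of this stands, and it limits the weight of the point. It does not make the ever-positive split the better method, and no planned output joins event onset to ADA onset.

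Three stronger readings are tempting but are not supported:

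- A reader might infer that the comparison is biased as it stands, or in a known direction. It is not biased with equal follow-up and no ADA effect. Otherwise, dilution and false excess pull opposite ways; in the table above, dropout partly offsets the dilution.
- A reader might take 75% as the size of the bias. It describes one subject first positive at Week 48. The documents give no distribution of first positivity.
- A reader might say that the misplaced events came before antibodies existed. The plan dates first detection only.

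The follow-up contrast should not be overstated either. Early leavers also give a withdrawal sample, possibly an SFU sample, and their TEAEs are counted for 140 days after the last dose.

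**Conclusion.** The point holds as a cheap improvement to a descriptive, exploratory table. That TEAEs preceding the first positive sample are counted as ADA-positive, and that Baseline-positive subjects without a titre rise share a stratum with treatment-induced positives, follows from the SAP's definitions and needs no assumption. The 6% to 75% window shares follow from the visit schedule. The size of any distortion does rest on assumptions: a false excess of 1.06 to 1.12 requires about 30% dropout, and dilution arises only if there is a real association. The primary efficacy conclusion is unaffected.

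**What to change.** Keep the existing table and add one to SAP Section 11.2:

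- Class each TEAE as before, or on/after, the subject's first treatment-induced ADA-positive sample, using the definition already in SAP Section 10.
- Divide subject-time at the same date, and give subject-time and exposure-adjusted rates for each part.
- Show Baseline-positive subjects without a titre rise on their own line.
- Use the actual sample date. SAP Section 4.4 assigns early-withdrawal ADA samples to the next scheduled ADA visit, which would date positivity too late.
- Repeat the table with onset dated to the preceding negative sample (for a Baseline-positive subject, the last sample before the required titre rise).

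Separately, reconcile Protocol Table 5-1 with Protocol Section 8.12 on whether ADA is sampled at the SFU Visit.

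The cost is SAP wording and modest programming on dates already collected. The main downside is that antibody onset lies somewhere between two samples 4 to 12 weeks apart on Table 5-1. The longest gap is 12/64 = 19% of a completer's window, so the added table can misplace events in the other direction. The repeat analysis shows how much that matters.

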### **11.3 Clinical laboratory evaluations**

Laboratory data (chemistry, hematology, and urinalysis) and changes from Baseline (if applicable) for numeric variables will be listed by treatment group and visit. Any laboratory variables that are BLQ or ALQ will be handled as described in [Section 4.2.3](#). Values outside the reference range for the numeric variables will be flagged in the listings and, in addition, will be listed separately. The reference ranges will also be reported in the listings.

Chemistry and hematology variables presented in [Table 11-1](#) will be summarized by treatment group at each visit, for both observed values and changes from Baseline. Figures of mean and mean change from Baseline will be presented by treatment for the absolute neutrophil count (ANC). All treatment groups will be overlaid on the same plot and the plot will include the error bars based on the SD (ie, mean +/-SD).

Laboratory variables will be grouped according to the laboratory function panel and categorized as normal, high or low, if applicable, based on the reference range supplied by the analytical laboratory. For selected variables that are identified in [Table 11-1](#), the change in category from Baseline will be presented in shift tables at all post-Baseline visits.

The number and percentage of subjects with treatment-emergent markedly abnormal (TEMA) values will be tabulated by treatment group and visit. Markedly abnormal laboratory values will generally be defined as those categorized as Grade 3 or Grade 4 as per the Rheumatology Common Toxicity Criteria (RCTC). Communication with the lead author of the RCTC publication has revealed that the reference ranges for absolute lymphocyte counts (ALC) are in error, therefore ALC criteria will follow the ranges defined as per the Common Terminology Criteria for Adverse Events (CTCAE) Version 4.03 (United States Department of Health and Human Services, 2010). Additional laboratory variables (not present in the RCTC publication) will also be categorized as per the CTCAE Version 4.03. The criteria for identifying TEMA values are presented in [Table 14-5](#) and [Table 14-6](#) for hematology and chemistry values respectively.

Laboratory measurements meeting the criteria for TEMA will be listed separately for hematology and chemistry. The listings will include all measurements for any variable with at least one TEMA result for each subject.

Any additional laboratory variables not included in the outputs described previously will be listed separately. These will include the following:

- Serology
- Urine drug screen
- Pregnancy tests (serum and urine)
- Follicle stimulating hormone (FSH) (only for women whose last menstrual cycle occurred between 12 and 24 months prior to the Screening Visit)
- The results of the Quantiferon tuberculosis (TB) Gold test will be listed separately.

Subjects with treatment-emergent liver function test abnormalities at any post-Baseline visit will be summarized (number and percentage of subjects) by treatment group. The criteria for this tabulation are presented in [Table 14–7](#).

